## 6.2.1 Potential Distant Spread of Toxin Adverse Events (Applicable to BOTOX Studies Only)

To assess possible distant spread of toxin (PDSOT), 40 MedDRA preferred terms that may be associated with botulinum toxin effects have been identified. All AEs associated with PDSOT will be tabulated by SOC and treatment group; in addition, all PDSOT AEs will be listed by subject. The 40 terms are listed below.

### MedDRA Preferred Terms Evaluated for Possible Distant Spread of Toxin

#### Cardiac Disorders

Bradycardia

#### Eye Disorders

Accommodation disorder  
Diplopia  
Extraocular muscle paresis  
Eyelid function disorder  
Eyelid ptosis  
Pupillary reflex impaired  
Vision blurred

#### Gastrointestinal Disorders

Constipation  
Dry mouth  
Dysphagia  
Ileus paralytic

#### Infections and Infestations

Botulism

#### Musculoskeletal and Connective Tissue Disorders

Muscular weakness

#### Nervous System Disorders

Bell's palsy  
Bulbar palsy  
Cranial nerve palsies multiple  
Cranial nerve paralysis  
Dysarthria  
Facial paralysis  
Facial paresis  
Hyporeflexia  
Hypotonia  
Paralysis  
Paresis cranial nerve  
Peripheral nerve palsy  
Peripheral paralysis  
Speech disorder  
Vocal cord paralysis  
Vocal cord paresis

#### Renal and Urinary Disorders

Urinary retention\*

#### Respiratory, Thoracic and Mediastinal Disorders

Aspiration  
Diaphragmatic paralysis  
Dysphonia  
Dyspnoea  
Pneumonia aspiration  
Respiratory arrest  
Respiratory depression  
Respiratory failure

#### Reproductive System and Breast Disorders

Pelvic floor muscle weakness

\*: The evaluation of events mapping to these terms will take into consideration the known mechanism of action of BOTOX, the temporal relationship of the event (time to onset of the AE), the duration of the event, any re-challenge information if applicable, confounding factors that may include co-morbidities, past medical history, concomitant medications and other non-specific constitutional symptoms of a patient. In accordance with this, since BOTOX is injected into the urinary bladder for this indication, and since urinary retention is considered an expected localized effect, the preferred term 'urinary retention' will not be considered a PDSOT event.

### 6.3 Serious Adverse Events

A treatment emergent SAE is an TEAE as defined above that further meets one or more SAE criteria at any time during the study treatment period.

The number and percent of patients with serious adverse events will be tabulated by treatment group for all serious adverse events and for treatment-related serious adverse events by SOC for each BOTOX treatment cycle. A listing will be generated of patients with serious adverse events.

### 6.4 Clinical Laboratory Evaluations

The clinical laboratory data (hematology, blood chemistry, and urinalysis) will be summarized by BOTOX treatment group for each BOTOX treatment cycle. Descriptive statistics will be generated for baseline values and change from study baseline by visit. Study baseline is defined as the last assessment prior to treatment 1.

Clinical laboratory test values will be considered potentially clinically significant (PCS) if they meet either the lower-limit or higher-limit PCS criteria. PCS criteria are specified on [Table 4](#). The number and percentage of patients who have PCS postbaseline clinical laboratory values will be tabulated for each cycle by treatment group. The percentages will be calculated relative to the number of patients with available non-PCS study baseline values and at least 1 postbaseline assessment during the treatment cycle of interest. The numerator will be the total number of patients with available non-PCS baseline values and at least 1 PCS postbaseline value during the treatment cycle of interest. A supportive listing of patients with PCS postbaseline values will be provided, including the patient number, baseline and all postbaseline (including non-PCS) values.

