6.3.14 Hematology and Clinical Chemistry

A blood sample for hematology and nonfasting clinical chemistry assays by a central laboratory will be taken at the time the IV line is started for general anesthesia prior to each treatment administration (if no general anesthesia is to be administered a blood sample is taken prior to treatment). A blood sample will also be taken at week 12 after each treatment and at study exit.

Analytes will be obtained as specified below, except for the week 12 sample where only complete blood count, blood urea nitrogen (BUN), and creatinine will be obtained:

- hematology: hemoglobin, hematocrit, RBC count, RBC morphology, WBC count, neutrophils, bands, lymphocytes, monocytes, basophils, eosinophils, and platelets
- blood chemistry: glucose, creatinine, BUN, total bilirubin, aspartate aminotransferase/serum glutamic oxaloacetic transaminase, alanine aminotransferase/serum glutamic pyruvic transaminase, alkaline phosphatase, uric acid, sodium, potassium, bicarbonate (carbon dioxide content), chloride, phosphorus, calcium, magnesium, and total protein

Laboratory results will be compared to age-appropriate normative values.

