**Table 2 Analysis Visit Windows**

Visit	Target Day of the Visit a	Study Visit Window a
Screening		≤ Day -1
Treatment 1 Day 1	1	Day 1
Treatment 1 Week 2	15	Day 2 – Day 29
Treatment 1 Week 6	43	Day 30 – Day 64
Treatment 1 Week 12	85	Day 65 – Day 127
Treatment 1 Week 24	169	Day 128 – Day 211
Treatment 1 Week 36	253	Day 212 – Day 295
Treatment 1 Week 48	337	Day 296 – Day 379
Treatment 1 Week 60	421	Day 380 – Day 463
Treatment 1 Week 72	505	Day 464 – Day 547
Treatment 1 Week 84	589	Day 548 – Day 631
Treatment 1 Week 96	673	Day 632 – Day 715/Exit
Treatment X Day 1	1	Day 1
Treatment X Week Y	Repeat same as treatment 1	Repeat same as treatment 1

a Study Day is relative to the most recent treatment day.

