## 2.3 Data Conventions

The following data conventions will be applied to all analyses:

- Only data with exceptions will be listed for conciseness. For example, the following would not be listed: normal findings for medical history and physical examination, pregnancy tests results for males or females when not applicable, etc.
- The level of significance used for all statistical tests will be 0.05, 2-sided, unless stated otherwise. P-values ≤0.050 will be considered as statistically significant.
- The type III sums of squares will be used for all analysis of covariance models (ANCOVA) and analysis of variance models (ANOVA).
- The variance for Kaplan-Meier estimates will be calculated using Greenwood's formula.
- Descriptive statistics for continuous variables will include the sample size (n), mean, standard deviation (SD), median, minimum (min), first quartile (Q1), third quartile (Q3), and maximum (max).
- Summary statistics for categorical variables will include the sample size (n), frequency count and percent.

- The Medical Dictionary for Regulatory Activities (MedDRA) dictionary will be used to code all adverse events (AEs) and medical history.
- World Health Organization Drug Dictionary Enhanced (WHO DDE) preferred name and MedDRA will be used to code all medications.
- Study duration from randomization/day 1 will be calculated as:  
$$\text{Study days} = \text{visit date} - \text{randomization/day 1 visit date} + 1.$$
- The Cycle duration for treatment X will be calculated as:  
$$\text{Study days} = \text{visit date} - \text{treatment X date} + 1.$$
- The algorithm presented in [Table 3](#), together with the rules below will be used to impute incomplete or missing dates for adverse events and medications as follows:
  - (a) AE start dates will be imputed as the minimum of the following:
    - initial imputed date, where target date = first study drug injection date.
    - complete end date
  - (b) Medication start dates will be imputed as the minimum of the following:
    - initial imputed date, where target date = first study drug injection date – 1.
    - complete end date
  - (c) AE and Medication end dates will be imputed as the minimum of the following:
    - initial imputed date, where target date = study exit date + 30.
    - Death date
- For each treatment cycle, AEs will be counted with onset date between the day when the study treatment is received and the day before the next treatment is received or exit day.

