## **6.1 Study Treatment – Exposure and Administration**

### **6.1.1 Exposure to Study Treatments**

The cumulative duration of treatment exposure will be summarized for the overall study and by each BOTOX treatment cycle. For each patient, the total duration of treatment exposure is defined as the number of days from the day of the first BOTOX treatment to the exit day or the day of data cut, as applicable. For each patient, the number of follow-up days for a given BOTOX treatment cycle is defined as the number of days from the day of treatment to the day prior to the subsequent treatment or exit day or the data cut day, as applicable.

Data will be presented in the following intervals: weeks  $\geq 2$  weeks,  $\geq 6$  weeks,  $\geq 12$  weeks,  $\geq 18$  weeks,  $\geq 24$  weeks,  $\geq 30$  weeks,  $\geq 36$  weeks,  $\geq 42$  weeks,  $\geq 48$  weeks,  $\geq 54$  weeks,  $\geq 60$  weeks,  $\geq 66$  weeks,  $\geq 72$  weeks,  $\geq 78$  weeks,  $\geq 84$  weeks,  $\geq 90$  weeks and  $\geq 96$  weeks. Duration of exposure is based on calendar weeks and descriptive summary statistics of the treatment duration in weeks will be presented.

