## 6.5 Vital Signs Measurements

Vital signs including pulse rate (beats/min), blood pressure (mm Hg), respiration rate (breaths per minute), and temperature (°C), will be summarized as descriptive statistics for baseline value and change from study baseline by BOTOX treatment group for each BOTOX treatment cycle.

Vital sign values will be considered potentially clinically significant (PCS) if they meet both the observed-value criteria and the change-from-baseline criteria. PCS criteria are specified on Table 5. The number and percentage of patients with PCS postbaseline values will be tabulated for each cycle by treatment group. The percentages will be calculated relative to the number of patients with available non-PCS study baseline values and at least 1 postbaseline assessment in the cycle of interest. The numerator will be the total number of patients with available non-PCS study baseline values and at least 1 PCS postbaseline value in the cycle of interest. A supportive listing of patients with PCS postbaseline values will be provided, including the patient number, baseline and all postbaseline (including non-PCS) values.

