### 6.6.7 Renal Function Testing

Renal function will be monitored from an estimate of the glomerular filtration rate (eGFR) determined from the serum creatinine levels obtained on the day of each treatment (prior to treatment), week 12 after each treatment, and at study exit. The calculation of eGFR will be based on  $eGFR = 0.41 \times \text{height (cm)}/\text{serum creatinine (mg/dL)}$ . For the derivation of estimated GFR, the height closest to the serum creatinine assessment will be used.

Summary statistics for mean values at each visit, study baseline and mean change from study baseline will be tabulated by treatment group. For study baseline eGFR, the latest value prior to the first treatment will be presented in the summary table.

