## 8. Immunogenicity Data Analyses

Two methods will be used to analyze immunogenicity samples: the enzyme linked immunosorbent assay (ELISA) method to detect the toxin-binding antibodies and the mouse protection assay (MPA) to detect the toxin-neutralizing antibodies to BOTOX. In the ELISA step, samples will be analyzed using a toxin-binding assay to determine the presence of any toxin-binding antibodies. Only samples from patients who are positive for the presence of toxin-binding assay will be subsequently analyzed using the MPA to determine the presence of toxin-neutralizing antibodies. For the toxin-binding assay, immunogenicity data will be reported as negative, positive or inconclusive. The percent of patients who have a serum sample that is positive for binding antibodies, as assessed by the screening and immunodepletion steps, will be reported by BOTOX treatment group at baseline, week 12 and study exit. The titer values for all samples will also be summarized.

The toxin-neutralizing data will be reported as protected, not protected, or inconclusive for the mouse protection assay (MPA). Samples considered protected are those that contain neutralizing antibodies towards BOTOX and thus protect the mouse from the lethal effects of BOTOX. Samples considered not protected do not protect the mouse from the lethal effects of BOTOX. The final result will depend on the number of mice found dead or alive. If 3 out of 4 mice or more are found dead then the sample will be considered negative (not protected) for neutralizing antibodies; if the number of dead mice is less than or equal to 1, then the sample will be considered positive (protected) for neutralizing antibodies; if 2 mice are found dead, or if the assay results or sample integrity are in question, then the sample will be considered as inconclusive. Antibody test results will be summarized and tabulated by BOTOX treatment group and by visit. The percent of patients considered protected, not protected, or inconclusive for toxin-neutralizing assay will be reported.

A listing of antibody assay results will be provided for patients who had a positive toxin-neutralizing antibody result.

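### Laboratory and vital-sign values taken before a repeat injection are counted in the PCS tables of the cycle that injection starts, leaving retreated patients with no scheduled cycle 1 value for 14 of 16 chemistry parameters

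*SAP*

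**What the plan says.** **Timing of the measurements.** Protocol 6.3.14 has blood drawn before each treatment, at week 12 after each treatment and at exit. The full panel is run each time "except for the week 12 sample where only complete blood count, blood urea nitrogen (BUN), and creatinine will be obtained". Protocol 6.3.4 and Table 1 place vital signs on a treatment day before the procedure.

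**Assignment to a cycle.** SAP Table 2 has a Treatment X Day 1 row and notes that "Study Day is relative to the most recent treatment day". In SAP 2.3, "The Cycle duration for treatment X will be calculated as" visit date minus treatment X date plus 1. SAP 6.1.1 defines follow-up in a cycle as "the number of days from the day of treatment to the day prior to the subsequent treatment or exit day" (or the data cut).

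**Counting.** SAP 6.4 defines study baseline as the last assessment before treatment 1. The PCS numerator needs "at least 1 PCS postbaseline value during the treatment cycle of interest" for laboratory tests and "at least 1 PCS postbaseline value in the cycle of interest" for vital signs. The denominator needs a non-PCS study baseline and at least one postbaseline assessment in the cycle. SAP 6 groups all of this by the dose actually received in that cycle.

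**Contrast.** For adverse events, SAP 6.2 requires onset, worsening or becoming serious after the cycle's treatment has begun. SAP 6.4 and 6.5 contain no equivalent condition.

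**The concern.** A blood sample or blood pressure taken minutes before the second injection cannot have been caused by it. It is the last observation under the first injection. The SAP's date arithmetic ignores clock time, so the value falls in cycle 2, and because no cycle-specific baseline exists it also counts as postbaseline there.

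Two things are at stake. First, cycle 1 is the only randomised comparison of the three doses. If the end-of-cycle sample leaves cycle 1, most chemistry parameters can be assessed there only in patients who exit without retreatment. That group is defined by what happened after dosing: it mixes patients who never asked for more treatment with early withdrawals and with patients exited because a lower dose was judged warranted (Protocol 5.5). Second, in a later cycle that is itself followed by retreatment, a patient counts as assessed for these parameters although the only scheduled value precedes that cycle's injection.

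**Working it through.** **1. The SAP's window rule reproduces.** SAP 2.2 sets each window from the midpoints between target days. For Treatment 1 Week 12 (target 85, neighbours 43 and 169):
- lower limit (85 + 43)/2 + 1 = 65
- upper limit (85 + 169)/2 = 127

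This matches Day 65 to Day 127 in Table 2.

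**2. Where the retreatment-day value lands.** Suppose treatment 2 is given on cycle 1 day d. Relative to treatment 2, the same date is d - d + 1 = 1, whatever d is. The value is therefore always Treatment 2 Day 1. SAP 6.1.1 agrees, since it ends cycle 1 the day before.

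**3. Whether it counts.** It is later than the last assessment before treatment 1, so it is postbaseline. It lies in cycle 2, so it enters the cycle 2 numerator and denominator under the cycle 2 dose.

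**4. Which measurements depend on it.** SAP Table 4 lists 16 chemistry parameters. Week 12 supplies two, BUN and creatinine: 16 - 2 = 14 are scheduled only before injections and at exit.

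| Measurement | Scheduled cycle 1 follow-up in a retreated patient, as written |
|---|---|
| 14 chemistry parameters | none |
| BUN, creatinine | week 12 |
| Hematology (CBC) | week 12 |
| Vital signs | weeks 2, 6 and 12, later clinic visits, qualification visit |

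A patient who exits without retreatment has the full panel at exit, and that falls in cycle 1.

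**5. Cycle 1 denominator for the 14 parameters.** Let N be the patients with a non-PCS baseline and r the share retreated. As written, the denominator is at most N x (1 - r); with the pre-injection sample kept in cycle 1 it is at most N. The documents do not give r, so a wide range is assumed. The planned total of 108, all doses together, serves only as a scale.

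| r (assumed) | As written, share of N | As written, if N = 108 | Sample kept in cycle 1, if N = 108 |
|---|---|---|---|
| 30% | 70% | 76 | 108 |
| 50% | 50% | 54 | 108 |
| 70% | 30% | 32 | 108 |
| 90% | 10% | 11 | 108 |

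All counts are upper bounds, with no missing samples.

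**6. A side effect any repair must avoid.** For laboratory variables SAP 2.2 keeps the last non-missing value in a window. A patient who qualifies at week 12 (Day 85) and is treated within 28 days is retreated by Day 85 + 28 = 113, inside Day 65 to 127. Simply renumbering the pre-injection sample as a cycle 1 day would let it displace the scheduled week 12 CBC, BUN and creatinine in the by-visit tables.

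**The case against.** The strongest reply is that SAP 6.4 and 6.5 never say that pre-injection values belong to the new cycle. That result comes from combining the windows, the cycle-day formula and the baseline definition. Treatment X Day 1 has its own row, so by-visit descriptive statistics keep these values apart from weeks 2, 6 and 12. The supporting listings show baseline and all postbaseline values for each patient with a PCS result, so the sequence can be traced. An abnormal laboratory finding can also be reported as an adverse event, and there the timing rule is sound.

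Much of this stands. It confines the problem to the per-cycle PCS tables. It does not remove it there, because the stated rules lead to one placement and no cycle baseline or exclusion points elsewhere. Listings do not restore a denominator.

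A reader might infer more than the documents support:
- *Cycle 1 has almost no chemistry follow-up.* This is true only of 14 parameters in retreated patients. BUN and creatinine have week 12 values, and patients who exit in cycle 1 have the full exit panel.
- *Abnormal values are always credited to the wrong dose.* The dose column changes only when the dose was increased.
- *Vital signs are affected to the same degree.* They have several scheduled visits in each cycle, so a retreatment-day value can add to the next cycle's numerator but the earlier cycle keeps its denominator.
- *eGFR and antibodies share the fault.* SAP 6.6.7 has no PCS table for eGFR, and week 12 creatinine supplies a cycle 1 value. In SAP 8 the binding-antibody percentage "will be reported by BOTOX treatment group at baseline, week 12 and study exit", but antibody results are also tabulated by visit and titers summarised for all samples.
- *The loss can be stated as patients per arm.* Planned arm sizes predate the agreed stop to recruitment (SAP 15), and the final numbers are not given.

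**Conclusion.** The point holds in a limited form. Under SAP 2.2, 2.3, 6.4 and 6.5 as written, laboratory and vital-sign values taken before the injection on a retreatment day count as postbaseline PCS data of the cycle that follows. The cycle is wrong every time. The dose column is wrong only after an escalation, and then always towards a higher dose, because Protocol 5.5 lets the dose only stay or rise.

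The effect is material mainly for 14 of the 16 chemistry parameters, where the cycle 1 PCS denominator shrinks to about N x (1 - share retreated) and holds a selected group. The size depends on two quantities absent from the documents, the share retreated and the final N, so only the formula and the illustrative range can be given. Unscheduled tests could add a few values. This should be settled before database lock, but it does not touch the efficacy analysis.

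**What to change.** Add to SAP 6.4 and 6.5: *For the per-cycle PCS tabulations, an assessment made before the injection on the day of treatment X (X of 2 or more) is assigned to cycle X-1 and to the dose received in cycle X-1, and is not counted as postbaseline in cycle X.*

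In by-visit summaries, show these values under a separate end-of-cycle / pre-retreatment label. They then stay out of the Week 12 window and cannot replace the scheduled week 12 result under the last-non-missing-value rule in SAP 2.2.

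Leave the adverse-event and exposure definitions of a cycle (SAP 2.3, 6.1.1, 6.2) as they are. Redefining every cycle to begin after the injection would conflict with them and is not needed.

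The cost is a few lines of SAP text and a change to the visit-assignment program, with no new data. SAP 1 plans one database lock after all patients exit, so the rule can be set before then. There is a small downside: end-of-cycle values fall at varying times after the dose, which the table footnotes should state.

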**Table 4 Clinical Laboratory PCS Criteria**

Laboratory Group	Parameter	SI Unit	PCS Low Limit	PCS High Limit
Hematology	Basophils, absolute cell count	10  /L	—	> 2.0 × ULN
	Eosinophils absolute cell count	10  /L	—	> 2 × ULN
	Hematocrit	%	< 0.9 × LLN	> 1.1 × ULN
	Hemoglobin	g/L	< 0.9 × LLN	> 1.1 × ULN
	Lymphocytes absolute cell count	10  /L	< 0.7 × LLN	> 1.3 × ULN
	Monocytes, absolute cell count	10  /L	< 0.5 × LLN	> 2.0 × ULN
	Neutrophils absolute cell count	10  /L	< 0.7 × LLN	> 1.5 × ULN
	Platelet count (thrombocytes)	10  /L	< 0.5 × LLN	> 1.5 × ULN
	Red blood cell count	10  /L	< 0.9 × LLN	> 1.1 × ULN
	White blood cell count	10  /L	< 0.9 × LLN	> 1.5 × ULN
Chemistry	Alanine aminotransferase	U/L	—	> 3 × ULN
	Alkaline phosphatase	U/L	—	> 1.2 × ULN: 5-11 years old > 3 × ULN: ≥ 12 years old
	Aspartate aminotransferase	U/L	—	> 3 × ULN
	Bicarbonate	mmol/L	< 0.9 × LLN	> 1.1 × ULN
	Bilirubin, total	µmol/L	—	> 1.5 × ULN
	Blood urea nitrogen	mmol/L	—	> 1.5 × ULN
	Calcium	mmol/L	< 0.9 × LLN	> 1.1 × ULN
	Chloride	mmol/L	< 0.9 × LLN	> 1.1 × ULN
	Creatinine	µmol/L	—	> 1.5 × ULN
	Glucose, nonfasting	mmol/L	< 0.8 × LLN	> 1.5 × ULN
	Phosphorus	mmol/L	< 0.9 × LLN	> 1.1 × ULN
	Potassium	mmol/L	< 0.9 × LLN	> 1.1 × ULN
	Magnesium	mmol/L	< 0.9 × LLN	> 1.1 × ULN
	Protein, total	g/L	< 0.9 × LLN	> 1.1 × ULN
	Sodium	mmol/L	< 0.9 × LLN	> 1.1 × ULN
Uric acid (urate)	µmol/L	—	> 1.2 × ULN	
Urinalysis	Glucose	µmol/L	—	Positive
	pH	—	< 0.9 × LLN	> 1.1 × ULN
	Protein	g/L	—	Positive
	Specific gravity	—	—	> 1.1 × ULN

LLN = lower limit of normal (value provided by the laboratory); SI = *Le Système International d'Unités* (International System of Units); ULN = upper limit of normal (value provided by the laboratory).

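### The PCS limit for urine specific gravity (1.1 × ULN) is at least 1.100 for any possible ULN, so this one row and its listing will be empty by construction

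*SAP*

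**What the plan says.** SAP 6.4 decides the flag from the limits in Table 4: "Clinical laboratory test values will be considered potentially clinically significant (PCS) if they meet either the lower-limit or higher-limit PCS criteria". For urine specific gravity, Table 4 leaves the unit and the low limit blank and gives one high limit: "Specific gravity — — > 1.1 × ULN". The table's footnote defines the reference value: "ULN = upper limit of normal (value provided by the laboratory". No number for it appears in the protocol or the SAP.

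The flag feeds two outputs. One is a count table: "The number and percentage of patients who have PCS postbaseline clinical laboratory values will be tabulated for each cycle by treatment group". Its numerator is the patients whose study baseline was not PCS and who have "at least 1 PCS postbaseline value during the treatment cycle of interest". The other is a supportive listing of the patients with such values.

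SAP 6.4 also plans a summary of the laboratory data, urinalysis included, that does not use the PCS limits: "Descriptive statistics will be generated for baseline values and change from study baseline by visit". I found no other rule for specific gravity in either document.

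**The concern.** A limit of 1.1 × ULN allows a 10% margin above normal. That is meaningful where the scale starts at zero, as for hemoglobin or hematocrit, which carry the same multiplier in Table 4. Specific gravity compares the density of urine with that of water. Water is 1.000, and the information lies in the second and third decimals. Ten percent of the whole number is about 0.10, several times the whole distance between water and a plausible ULN.

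If no urine sample can exceed the limit, the row shows 0% for 25 U, 50 U and 100 U in every cycle. A reader of the safety tables could take that as evidence of no abnormality and no dose relation, when no data could have produced another number. At stake is the interpretation of one descriptive safety row, not a test or a decision rule.

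**Working it through.** **Inputs**

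- Multiplier: 1.1, high side only (SAP Table 4).
- ULN: supplied by the laboratory and not stated. Assumed 1.020 to 1.040, with water (1.000) as the extreme case.
- Highest attainable urine specific gravity, M: not stated. Assumed anywhere from 1.035 to 1.080.

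The plan states only the multiplier and no numeric limit, so there is no figure of its own to reproduce.

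**Step 1: the limit.** Limit = 1.1 × ULN. To see it on the part of the scale that varies, compare the excess over water: (limit − 1) / (ULN − 1).

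| Assumed ULN | Limit = 1.1 × ULN | Limit − 1 | ULN − 1 | Ratio |
|---|---|---|---|---|
| 1.020 | 1.122 | 0.122 | 0.020 | 6.1 |
| 1.025 | 1.1275 | 0.1275 | 0.025 | 5.1 |
| 1.030 | 1.133 | 0.133 | 0.030 | 4.4 |
| 1.035 | 1.1385 | 0.1385 | 0.035 | 4.0 |
| 1.040 | 1.144 | 0.144 | 0.040 | 3.6 |

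To be flagged, a sample would need 3.6 to 6.1 times the excess over water that the laboratory regards as the top of normal.

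**Step 2: a bound that needs no laboratory figure.** With ULN ≥ 1.000, limit ≥ 1.1 × 1.000 = 1.100. The result therefore does not hinge on which ULN the laboratory supplies. Nor does the reporting format matter: a ULN written as 1030 gives 1.1 × 1030 = 1133, the same point on the scale.

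**Step 3: the inverse.** For a sample at M to exceed the limit, the ULN must be below M / 1.1.

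| Assumed M | ULN needed for a flag |
|---|---|
| 1.035 | below 0.941 |
| 1.040 | below 0.945 |
| 1.050 | below 0.955 |
| 1.060 | below 0.964 |
| 1.080 | below 0.982 |

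Every required ULN lies below water. Even the most generous assumed maximum falls short of the lowest possible limit by 1.100 − 1.080 = 0.020.

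**Step 4: the outputs.** Under these assumptions no baseline value can be PCS, so every patient with a baseline and a later value in the cycle enters the denominator. No later value can be PCS either, so the numerator is 0. The row reads 0/n = 0% in each cycle and dose group, and the listing has no entry for this parameter.

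**The case against.** Several points on the other side are sound.

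- **The attainable maximum is not in the documents.** It would be easy to state flatly that urine cannot reach the limit. The protocol and SAP do not say so. The conclusion needs an assumed maximum, and is shown here for 1.035 to 1.080. What needs no assumption about the laboratory or the patients is only that the limit is at least 1.100.
- **A shift in specific gravity would not go unseen.** A reader might infer that the trial could not detect one. The documents do not support that: SAP 6.4 also summarizes urinalysis values and their change from study baseline by visit, dose group and cycle.
- **The blank low limit is not a fault.** It might look like a second error that the parameter cannot be flagged low. Many Table 4 rows are one-sided, including alanine aminotransferase, total bilirubin, creatinine and uric acid. It matters only in that nothing else can put a patient in this row.
- **Nothing depends on the row.** No hypothesis test, stopping rule or treatment criterion uses it. Urinary and renal safety are covered elsewhere in the SAP: urinary tract infection by period (6.2), post-void residual volume (6.6.3), catheterization (6.6.4), ultrasound (6.6.5), urine culture (6.6.6) and eGFR (6.6.7).
- **The limit may be a sponsor standard.** SAP section 15 attributes the PCS definition to company standards. The table also keeps an alkaline phosphatase limit for ages 5 to 11, although the protocol enrols ages 12 to 17. That is consistent with a table taken over without full tailoring. It explains how the row could arise but does not make the limit work.

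These points limit the consequence. None of them makes the limit reachable.

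**Conclusion.** The concern holds, as a minor point. Followed exactly, the Table 4 rule sets a limit of at least 1.100, and 1.122 to 1.144 for an assumed ULN of 1.020 to 1.040. Provided that the highest attainable urine value lies anywhere from 1.035 to 1.080, the specific gravity row is zero and its listing empty in every cycle and dose group, independent of the data.

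This is a poorly chosen threshold in a stated rule, not a miscalculated figure or a missing detail. It affects one row of the PCS table and the matching part of the listing. The other rows of Table 4, the descriptive statistics for specific gravity and all efficacy results are untouched.

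**What to change.** Change the specific gravity row in SAP Table 4 in one of two ways.

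1. **Delete the row** from the PCS table and rely on the descriptive statistics in SAP 6.4. This needs no outside figure and removes the uninformative zero.
2. **Set the limit directly on the specific gravity scale**, for example a value above the laboratory ULN, or an absolute value that the sponsor justifies. Flagging everything above the ULN is an ordinary out-of-range flag, so the sponsor should say whether that is what PCS is meant to convey here.

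It may be tempting to keep the 10% and apply it to the excess over 1.000. For an assumed ULN of 1.030 that gives 1.000 + 1.1 × 0.030 = 1.033, only 0.003 above the ULN. Nothing in the documents supports such a difference as potentially clinically significant, so I would not propose it.

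The cost is one table cell and about one line of programming, plus a departure from the sponsor's standard table if the limit comes from there. With a reachable limit, some flags will reflect hydration only; their number cannot be estimated from the documents. Deleting the row avoids that.
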